15.2.3. Secondary Analysis

Safety analysis: To assess clinical safety, adverse events, vital sign measurements, and clinical laboratory information will be summarized. Adverse Events will be coded using the Medical Dictionary for Regulatory Activities (MedDRA). Changes from baseline for clinical laboratory values and vital signs will be summarized over time. Descriptive statistics and shift tables will be generated as appropriate.

The **secondary efficacy/pharmacodynamic analysis** will be performed using the ITT and EE populations and will include:

- Erythroid response, as defined above for primary endpoint, performed using the ITT population.
- For non-transfusion dependent patients, the proportion of patients with an increase of ≥ 1.0 g/dL from pretreatment hemoglobin maintained ≥ 8 weeks.
- For non-transfusion dependent patients, the proportion of patients with an increase of ≥ 1.5 g/dL from pretreatment hemoglobin maintained ≥ 8 weeks.
- For transfusion dependent patients, the proportion of patients who have $\geq 50\%$ reduction in RBC transfusion burden compared to pretreatment using 12-week intervals.
- For transfusion dependent patients, the proportion of patients who have $\geq 50\%$ reduction in RBC transfusion burden compared to pretreatment using 8-week intervals.
- For transfusion dependent patients, the proportion of patients who have no RBC transfusions ≥ 8 weeks.
- Time to erythroid response and duration of erythroid response.
- Change from pretreatment in transfusion burden in transfusion dependent patients
- Change in hemoglobin level in non-transfusion dependent patients
- Change in pre-transfusion hemoglobin levels in transfusion dependent patients
- Change from baseline in erythropoiesis parameters including serum erythropoietin levels, hemoglobin analysis (electrophoresis, globin chain RNA), reticulocytes, and nucleated RBCs
- Change from baseline in hemolysis parameters include haptoglobin, indirect bilirubin, and lactate dehydrogenase (LDH)
- Change from baseline in iron metabolism parameters include serum iron, total iron binding capacity (TIBC), transferrin, calculated transferrin saturation, soluble

transferrin receptor, ferritin, non-transferrin bound iron (NTBI), hepcidin, and liver iron content (LIC) by MRI

- Change from baseline in bone metabolism parameters include bone specific alkaline phosphatase (BSAP) and C-telopeptide of type I collagen (CTX)

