15.5. Deviation from Original Analysis Plan

A formal Statistical Analysis Plan (SAP) for the analysis and presentation of data from this study will be prepared before the database lock. Deviations from the statistical analyses outlined in this protocol will be indicated in this plan; any further modifications will be noted in the final clinical study report.

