5. STATISTICAL METHODOLOGY

5.1. Definitions

Transfusion Dependent (TD)

Based on protocol, TD patients are defined as those who required ≥ 4 units of RBCs every 8 weeks (confirmed over 6 months prior to Cycle 1 Day 1).

For programming implementation, a patient is defined as TD if the total RBCs is ≥ 11 units during 26 weeks on or prior to Cycle 1 Day 1.

Non-Transfusion dependent (NTD)

NTD patients are those who do not meet the above definition for TD. For programming implementation, NTD patients are defined as those who received < 11 units of RBCs during 26 weeks on or prior to Cycle 1 Day 1.

Baseline Hemoglobin

Baseline hemoglobin will be an average of hemoglobin measurements within 28 days of Cycle 1 Day 1, excluding measurements within 14 days following RBC transfusion.

Baseline Transfusion Burden

Baseline transfusion burden will be calculated as the total amount of RBC transfusions during the 12 weeks on or prior to Cycle 1 day 1.

Baseline for Other Parameters

Baseline erythropoietin (EPO) is defined as the maximum test value within 28 days of Cycle 1 Day 1. For all other parameters, baseline is defined as the last observation on or prior to Cycle 1 Day 1.

Transfusion Unit Conversion

The transfusion amount measured in unit “mL” will be converted to “units” according to medical review.

End of Treatment (EOT)

Procedures and evaluations for the end of treatment visit should be performed 28 days (± 7 days) after the last dose of ACE-536.

End of Study (EOS)

Procedures and evaluations for the end of study visit should be performed 28 days (± 7 days) after the Day 113/EOT visit (56 days after the last dose of ACE-536).

Combined Dose Groups

Low dose group includes patients on 0.2mg/kg and 0.4 mg/kg dose cohorts. High dose group include patients with dose level 0.6 mg/kg and above. Suitable summaries may be presented by low/high dose as specified.

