5.7. Efficacy Analyses

All efficacy endpoint will be performed using the ITT population.

All efficacy summaries will be presented by dose cohort and for NTD and TD patients separately. In addition, the dose cohorts will be combined and presented as low dose group and high dose group. Low dose group includes patients on 0.2 and 0.4 mg/kg dose cohorts. High dose group includes patients on 0.6 mg/kg and above. No formal hypothesis testing is planned.

In general, below rules apply to the derivations of efficacy endpoints which utilize hemoglobin and RBC transfusion data unless specified otherwise:

- Hemoglobin measurements within 14 days following RBC transfusion will be excluded from efficacy analysis
- For each patient, all efficacy endpoints will be derived based on an analysis cut-off day, defined as the last dose + 56 days or the last date from transfusion record data, whichever is earlier.

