5.7.1. Primary Efficacy Endpoint

The primary efficacy endpoint is the proportion of β -thalassemia patients who have an erythroid response, defined as below:

- For non-transfusion dependent (NTD) patients, a hemoglobin increase of ≥ 1.5 g/dL from baseline sustained for ≥ 14 days (in the absence of RBC transfusions). Hemoglobin measurements within 14 days following RBC transfusion or after 56 days of last dose will be excluded from analysis.
- For transfusion dependent (TD) patients, a $\geq 20\%$ reduction in RBC transfusion burden during any rolling 12-week window on treatment compared to baseline. The rolling 12-week window starts on Day 1 and increments by 1 day, e.g., from day 1 to day 84, day 2 to day 85, day 3 to day 86, etc. The search window ends on last dose day + 56 days or last day of hemoglobin measurement, whichever is earlier.

A point estimate of the proportion of patients having a response will be presented along with its associated exact 95% confidence interval based on binomial distribution for NTD and TD patients separately.

The complete hemoglobin measurements and RBC transfusion records will be listed for each patient.

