5.7.2. Secondary Efficacy Endpoints

5.7.2.1. Modified Erythroid Response

Modified erythroid response rates will be defined as below for NTD and TD patients.

For non-transfusion dependent (NTD) patients:

- The proportion of patients with a mean increase of ≥ 1.0 g/dL from pretreatment hemoglobin during any rolling 8 weeks.
- The proportion of patients with a mean increase of ≥ 1.5 g/dL from pretreatment hemoglobin during any rolling 8 weeks.
- The proportion of patients with a mean increase of ≥ 1.0 g/dL from pretreatment hemoglobin during any rolling 12 weeks
- The proportion of patients with a mean increase of ≥ 1.5 g/dL from pretreatment hemoglobin during any rolling 12 weeks

For transfusion dependent (TD) patients:

- The proportion of patients who have $\geq 50\%$ reduction in RBC transfusion burden compared to pretreatment using 12-week intervals.
- The proportion of patients who have $\geq 50\%$ reduction in RBC transfusion burden compared to pretreatment using 8-week intervals.
- The proportion of patients who have no RBC transfusions ≥ 8 weeks.

For each of the above defined modified erythroid response rate, a point estimate will be presented along with the exact 95% confidence interval based on binomial distribution.

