5.13. Changes in Conduct or Planned Analyses from the Protocol

Major changes between SAP and the planned analysis in Protocol Amendment 4 are described below:

Changes	Rationale
Definition of baseline hemoglobin	Protocol definition: Baseline hemoglobin will be the average of at least two measures (not influenced by transfusion within 7 days of measurement); one measure performed within one day prior to Cycle 1 Day 1 and the other performed 7-28 days prior to Cycle 1 Day 1. This definition is revised in this SAP to reflect the derivation rule implemented for this study.
Remove Efficacy Evaluable (EE) population	EE population is very similar to ITT population. ITT provides more conservative estimate of treatment effect.

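### SAP 5.7.2.1 replaces the protocol's NTD endpoint of a hemoglobin increase maintained for at least 8 weeks with a rolling 8-week mean, keeps no maintained analysis, and does not declare the change in 5.13

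*SAP*

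**What the plan says.** Protocol 15.2.3 (and the synopsis) lists two NTD secondary endpoints, one at 1.0 g/dL and one at 1.5 g/dL. Each is the proportion of patients whose increase "from pretreatment hemoglobin maintained ≥ 8 weeks". The protocol does not say what *maintained* means when a value dips or is missing.

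SAP 5.7.2.1 keeps both thresholds and the 8 weeks, but counts a patient whose mean increase reaches the threshold "from pretreatment hemoglobin during any rolling 8 weeks". It adds the same two rules over 12 weeks. No maintained version remains.

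Protocol 15.5 states: "Deviations from the statistical analyses outlined in this protocol will be indicated in this plan". SAP 5.13 opens with "Major changes between SAP and the planned analysis in Protocol Amendment 4 are described below" and has two entries: the definition of baseline hemoglobin and the removal of the efficacy-evaluable population.

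**The concern.** A requirement on duration has become a requirement on an average. Values below the threshold now count towards a response as long as higher values offset them. The SAP does not appear to be merely spelling out *maintained*: for the primary NTD endpoint, in 5.7.1, it still uses a sustained rule (14 days). The heading of 5.7.2.1 does not disclose the change either, because the TD endpoints under the same heading match the protocol.

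At stake is a reported secondary response rate that no longer answers the protocol's question, with no stated reason. The mean rule also carries into SAP 5.7.2.2, where NTD time to response and duration of response rest on a 12-week rolling mean of at least 1.0 g/dL. Finally, 5.7.2.1 sets no minimum number of values per window. Days 8 to 63 hold eight scheduled hematology visits after baseline. The last possible window, Days 86 to 141, holds four (Days 92, 99, 113 and 141), before any values are lost to the post-transfusion exclusion.

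**Working it through.** **The plan's own figure.** Neither document gives an expected rate or a power for this endpoint. The only related figure is the power of about 87% for the primary endpoint (n = 30, one-sided 0.05, 30% versus 10%). With a continuity-corrected normal approximation:

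Φ[(0.20 − 1/60 − 1.645·√(0.09/30)) / √(0.21/30)] = Φ(0.0932/0.0837) = 86.7%.

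The figure reproduces and does not involve the 8-week endpoint.

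**Direction.** Read *maintained* as: every non-excluded value is at or above baseline plus the threshold, over a run of at least 56 days. Any 8-week window inside that run has a mean at or above the threshold. Every maintained responder is therefore a rolling-mean responder. The converse fails: weekly changes of 0.2, 0.4, 0.8, 1.2, 1.6, 1.6, 1.2 and 1.0 sum to 8.0, so their mean is 8.0/8 = 1.0 g/dL. That patient responds under the SAP, yet only 5 of the 8 values reach 1.0 and that run spans 4 weeks. If one dip is allowed, the nesting is no longer a logical certainty, because a single deep dip can pull the mean below the threshold.

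**Size, by simulation (40,000 patients per scenario).**

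Inputs from the documents:
- Hematology visits weekly from Day 8 to Day 99, then Days 113 and 141 (schedule of events).
- Search up to a cut-off "defined as the last dose + 56 days or the last date from transfusion record data, whichever is earlier", which is about Day 141 for a last dose on Day 85.
- "Baseline hemoglobin will be an average of hemoglobin measurements within 28 days of Cycle 1 Day 1", taken here as two values.

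Assumptions not in the documents:
- Within-patient SD of 0.1 to 0.6 g/dL.
- True change across patients distributed N(1.0, 0.7²) g/dL.
- An effect that ramps up and then wanes after dosing, or one that is constant.

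Cohort results, ramp profile:

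| Threshold (g/dL) | Within-patient SD | Maintained, all values | Maintained, one dip allowed | Rolling mean | Rolling mean ÷ all values | Rolling mean ÷ one dip |
|---|---|---|---|---|---|---|
| 1.0 | 0.1 | 42.9% | 46.0% | 51.4% | 1.2 | 1.1 |
| 1.0 | 0.6 | 22.6% | 35.6% | 60.2% | 2.7 | 1.7 |
| 1.5 | 0.1 | 18.8% | 20.9% | 25.2% | 1.3 | 1.2 |
| 1.5 | 0.6 | 8.8% | 16.3% | 36.0% | 4.1 | 2.2 |

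With a constant effect, the ratio to the all-values rule is 1.2 to 2.3 at 1.0 g/dL and 1.3 to 3.2 at 1.5 g/dL. No simulated patient was an all-values responder without also being a rolling-mean responder.

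**Where the gap comes from.** For patients whose true change equals the threshold, 7–17% respond under the all-values rule and 62–72% under the rolling mean. For a true change 0.5 g/dL above the threshold, the rules agree at SD 0.1 (100% each) but give 36–50% versus 93–95% at SD 0.6. With no true change, the rolling mean counts at most about 6% at 1.0 g/dL (all values: at most 0.2%) and at most 0.5% at 1.5 g/dL (all values: 0%).

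**The case against.** - **The comparator is a choice.** The protocol leaves *maintained* undefined, so the all-values rule is one reading and not the protocol's text. A rolling mean could be offered as a workable definition. This stands as a limit on the size, and it is why the one-dip results are shown. It does not remove the need to declare the change.
- **A reader might infer that the SAP greatly inflates the response rate.** The documents do not support that. They give no within-patient SD and no spread of effects, and the assumed range starts at ratios of 1.1 to 1.2. *Inflates* also treats the strict rule as the truth. With noisy values, that rule misses half or more of the patients whose true change is 0.5 g/dL above the threshold. The mean rule trades specificity for sensitivity.
- **Searching for the best window is not in itself the difference.** The protocol fixes no particular 8 weeks either, and the maintained rule in the simulation accepts any qualifying run.
- **A reader might infer that the rate would be mistaken for sustained response.** The SAP's title for the section, and its reference to a mean in any rolling window, say otherwise.
- **A reader might suspect a data-driven change,** since the SAP is dated August 2017 in an open-label study with periodic review of response data. Nothing in the documents shows this.
- **Non-declaration.** SAP 5.13 claims to cover only major changes; protocol 15.5 has no such limit. SAP 5.13 also attributes to Amendment 4 a baseline definition (second value 7 to 28 days before Cycle 1 Day 1, 7-day transfusion rule) that differs from protocol 15.2.2 as supplied (Day −28 to Day −1, 2 weeks). The SAP may therefore have been compared with another protocol version. This stands and must be checked.
- **Impact is limited.** The endpoint is secondary, descriptive and untested, and all hemoglobin values will be listed per patient, so any definition can be derived later.

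**Conclusion.** The substitution and its absence from SAP 5.13 are established by the two texts, subject to confirming the protocol version. Under the all-values reading, the direction is certain: the SAP rate equals or exceeds the protocol rate. The size cannot be fixed from the documents. For cohorts with mean true change 1.0 g/dL, between-patient SD 0.7 g/dL and within-patient SD 0.1 to 0.6 g/dL, the ratio runs from about 1.2 to about 4; at the 1.0 g/dL threshold with one dip allowed, it runs from about 1.1 to 1.7. The primary endpoint and its stated 87% power are not affected. This should be corrected, but it does not threaten the trial's main result.

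**What to change.** 1. In SAP 5.7.2.1, report the protocol's two endpoints at 1.0 and 1.5 g/dL with *maintained* defined explicitly. One workable definition is that all non-excluded values are at or above baseline plus the threshold over a span of at least 56 days, with a version allowing one dip as a sensitivity analysis. State how missing values are handled.
2. Report the 8- and 12-week rolling means beside them, labelled as added in the SAP, and set a minimum number of values per window.
3. Confirm which protocol version the SAP was compared with, then list and justify the change in 5.13.

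The cost is SAP wording and one extra derivation from data already collected. On the all-values definition, the protocol-defined rate will be equal to or lower than the rolling-mean rate, so it is likely to look less favourable.

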5.7.2.2. Time to and Duration of Erythroid Response

Time to and duration of erythroid response will be analyzed for erythroid responders defined as below:

- For NTD patients, mean increase of ≥ 1.0 g/dL from pretreatment hemoglobin during any rolling 12 weeks
- For TD patients, $\geq 50\%$ reduction in RBC transfusion burden compared to pretreatment using 12-week intervals.

Time to erythroid response will be defined as the time from the first dose date to the first date of any rolling 12-week window achieving above erythroid response.

Duration of erythroid response will be defined as the time from the starting date of the first rolling 12-week window achieving response to the last date of the consecutive rolling 12-week window achieving response. When there are multiple disjoint intervals with response, the longest interval will be used. Patients with response ongoing by the analysis cutoff day will be censored.

Both time to and duration of erythroid response will be analyzed as continuous variables and summarized by descriptive statistics. In addition, duration of erythroid response will also be analyzed as a time to event endpoint.

The derivations of time to and duration of erythroid response will be listed for each patient.

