8. TRIAL OBJECTIVES

8.1. Primary Objective

- To evaluate the proportion of β -thalassemia patients who have an erythroid response, defined as: 1) a hemoglobin increase of ≥ 1.5 g/dL from baseline for ≥ 14 days (in the absence of red blood cell [RBC] transfusions) in non-transfusion dependent patients, or 2) $\geq 20\%$ reduction in RBC transfusion burden compared to pretreatment in transfusion dependent patients

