8.2. Secondary Objectives

- To evaluate safety and tolerability of ACE-536
- To evaluate the proportion of transfusion dependent patients who have $\geq 50\%$ reduction of RBC transfusion burden compared to pretreatment
- To evaluate the time to erythroid response and duration of erythroid response
- To evaluate the change in hemoglobin level in non-transfusion dependent patients
- To evaluate the change in pre-transfusion hemoglobin levels in transfusion dependent patients
- To evaluate changes in biomarkers of erythropoiesis, hemolysis, iron metabolism, and bone metabolism
- To examine the pharmacokinetic (PK) profile of ACE-536 in patients with β -thalassemia

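### SAP 5.7.2.2 times two modified response criteria, not the protocol's erythroid response; time to response is summarised in responders only, and SAP 5.13 does not list the change

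*SAP*

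**What the plan says.** **Protocol.** Section 8.2 sets the objective: "To evaluate the time to erythroid response and duration of erythroid response". Section 15.2.3 lists the matching analysis, "Time to erythroid response and duration of erythroid response", without a separate definition. The only definition of erythroid response is the primary one (8.1 and 15.2.2): "a hemoglobin increase of ≥ 1.5 g/dL from baseline for ≥ 14 days" without transfusion in NTD patients, or a burden reduction of at least 20% in TD patients. Section 15.2.3 closes by planning Kaplan-Meier curves, medians and 95% confidence intervals for secondary endpoints of time-to-event type. Section 15.5 says the SAP will indicate departures from the protocol's analyses.

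**SAP.** Section 2 repeats the objective, and 5.7.1 keeps the protocol's response as the primary endpoint. Section 5.7.2.2 states "Time to and duration of erythroid response will be analyzed for erythroid responders defined as below" and gives two other criteria:

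- NTD: mean hemoglobin rise of at least 1.0 g/dL over any rolling 12 weeks.
- TD: burden reduction of at least 50% over 12-week intervals.

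Both come from the list in 5.7.2.1 that opens "Modified erythroid response rates will be defined as below for NTD and TD patients". Time to response is "the time from the first dose date to the first date of any rolling 12-week window achieving above erythroid response". Time and duration are both summarised descriptively; in addition, "duration of erythroid response will also be analyzed as a time to event endpoint". Sections 4.1 and 5.7 use the ITT population for all efficacy analyses. Section 5.13 lists two changes, the baseline hemoglobin definition and removal of the efficacy evaluable population.

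**The concern.** A table titled time to or duration of erythroid response will be read as describing the response whose rate is reported under 5.7.1. Under the SAP it describes a different one. Some patients counted as primary responders will have no time or duration, and some patients with a time and duration will not be primary responders (for example, an NTD patient steady at +1.2 g/dL). No other SAP section times the protocol's response, so a named secondary objective would go unanswered. Because time to response is restricted to responders, the planned summary also says nothing about how quickly response accrues among all treated patients.

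**Working it through.** **1. Text comparison**

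| Item | Protocol | SAP 5.7.2.2 |
|---|---|---|
| NTD response timed | ≥1.5 g/dL for ≥14 days | 12-week mean rise ≥1.0 g/dL |
| TD response timed | ≥20% burden reduction | ≥50% burden reduction, 12 weeks |
| Time to response | Kaplan-Meier, if read as time-to-event | Descriptive, responders only |
| Duration | Kaplan-Meier, if read as time-to-event | Descriptive, and also time-to-event |
| Listed in SAP 5.13 | – | No |

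The TD criterion is a protocol secondary endpoint, but not the protocol's erythroid response. The NTD criterion is not in the protocol; the nearest item is "the proportion of patients with an increase of ≥ 1.0 g/dL from pretreatment hemoglobin maintained ≥ 8 weeks". Protocol 15.2.3 does not name its time-to-event endpoints, but time to and duration of response are the only items of that type in its list.

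**2. Range of the reported variables.** Assume last dose on Day 85 and cut-off at last dose + 56 = Day 141 (SAP 5.7). A 12-week window is 84 days, so the latest one starts on Day 141 − 83 = 58. Time to response is then at most 58 − 1 = 57 days (59 if the last dose is on Day 87). Duration is at least 84 days counted inclusively, whereas a primary NTD response may last 14.

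**3. NTD primary responders who would not be timed.** Assumptions: hematology on Days 1, 8, 15, …, 99, 113 and 141 (schedule of events); a simple mean of the values in each window; windows starting on Days 1 to 58. Each such window holds m = 8 to 12 values. Suppose k consecutive visits are at +1.5 g/dL and all other values at b. Three weekly visits span 14 days, so k = 3 can already be a primary response. If all k visits lie in the window:

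mean = b + k(1.5 − b)/m, which is ≥1.0 only if m ≤ k(1.5 − b)/(1 − b).

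- b = 0: m ≤ 1.5k, that is 4.5, 6 and 7.5 for k = 3, 4 and 5. No window has fewer than 8 values, so the criterion is met in 0 of 14, 0 of 13 and 0 of 12 placements. With k = 6 it is met in 5 of 11, with k = 7 in 5 of 10, and with k = 8 in all 9.
- b = +0.5: m ≤ 2k. Met in 0 of 14, 6 of 13 and 7 of 12 for k = 3, 4 and 5, and in all placements from k = 6.
- b = +0.8: m ≤ 3.5k. Met in 9 of 14 for k = 3 and in all placements from k = 4.

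**4. TD primary responders who would not be timed.** A patient on 2 units every 21 days has 8 units in 84 days. One missed transfusion leaves 6, and (8 − 6)/8 = 25%. That meets the 20% rule; the timed rule needs 4 units or fewer.

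**5. A caution about timing the 20% rule.** Take an unchanged 2 units every 22 days, with the last transfusion 8 to 22 days before Day 1 (15 timings; transfusion within the previous 7 days is an exclusion). An 84-day period holds either 4 or 3 transfusions, 8 or 6 units. Where the baseline holds 8 and some later window holds 6, the rule is met at 25% with no real change. This happens in 11 of 15 timings if baseline ends the day before Day 1 (gaps 8–18), and also in 11 of 15 if it ends on Day 1 (gaps 8–17 and 22). The 50% rule is met in none.

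**The case against.** The strongest reply is that the SAP's choices are visible and partly sensible.

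- **TD criterion.** The 50% reduction is a protocol secondary endpoint, and step 5 shows the 20% rolling rule can be met by an unchanged rhythm. This stands. A reader might infer that timing 50% is unsupported; the documents do not bear that out.
- **Responders only.** Restricting duration to responders is normal, and duration is already also analysed as time-to-event with censoring at the cut-off. Response rates with exact intervals in ITT show the non-responders. This stands for duration. For time to response, it leaves the protocol's Kaplan-Meier plan unmet.
- **Size of the NTD loss.** A short rise on a zero background is an extreme case. This stands: at +0.8 elsewhere, most three-visit responses and all longer ones are timed. A reader might infer that many NTD responders will be lost; the documents give no basis for a frequency.
- **Disclosure.** SAP 5.13 covers major changes only, and the criteria are set out openly in 5.7.2.2. A reader might infer concealment; the text does not support that. But replacing the response behind a named secondary objective is a major change, and it is neither flagged nor explained.
- **Dating.** A reader might take dating at the start of the window as an error. It is a stated convention, and the protocol sets no other.

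**Conclusion.** The point holds. SAP 5.7.2.2 does not deliver time to or duration of the response that the protocol defines, it omits the planned Kaplan-Meier analysis for time to response, and 5.13 does not record either change. This rests on the wording alone. The counts rest on scheduled visits, a simple mean per window and last dose on Day 85; they show that the mismatch can occur, not how often it will.

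The weight is moderate. The primary endpoint is untouched, every analysis is descriptive, and hemoglobin values, transfusion records and timing derivations are listed per patient. The change should still be made, because otherwise a secondary objective is reported under a name that belongs to a different response.

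**What to change.** 1. In SAP 5.7.2.2, add time to and duration of the 5.7.1 response, dating NTD onset at the first hemoglobin value of the qualifying run of at least 14 days. Keep the present analysis, labelled as modified response.
2. For TD, keep the 50% timing. If the 20% timing is added, state that an unchanged rhythm can meet the 20% rolling rule, with the 22-day example. If it is not added, say so and why in 5.13.
3. Add Kaplan-Meier for time to response in all ITT patients, censoring non-responders at the cut-off, beside the responders-only summary. Present it within NTD and TD where the SAP 5.2 rule of more than 5 patients is met. The expansion cohort meets it, with at least 12 of each type; a single escalation cohort of 5 or 6 meets it only if six patients are all of one type.
4. List the change and its rationale in SAP 5.13.

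The cost is SAP wording and some reprogramming from data already collected. The limitation to accept is that TD onset is known only to within the 84-day window.
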